Psychogenic non-epileptic seizures (PNES) are common, highly disabling, and can be readily diagnosed via the gold standard video-EEG monitoring. Several studies, including two randomized clinical trials have demonstrated the efficacy of psychotherapy (and particularly cognitive behavioral therapy) in treating PNES. However the majority of patients with PNES do not complete psychotherapy and continue to suffer from seizures, disability, social dependence, and increased healthcare resource utilization over the long term. One important barrier to treatment is a high rate of non-adherence with psychotherapy among patients with PNES. This study will entail a randomized trial of motivational interviewing to improve adherence with psychotherapy among patients with PNES. Motivational interviewing is a counseling style that was originally developed to help recovering alcoholics refrain from risky alcohol consumption and has subsequently been extensively studied and used in treating substance abuse, promoting weight loss in obese patients, and improving adherence with treatment among patients with HIV, schizophrenia, and other disorders.

RESEARCH DESIGN AND METHODS

Briefly describe study design and anticipated enrollment, i.e., number of subjects to be enrolled by researchers study-wide and by Partners researchers. Provide a brief summary of the eligibility criteria (for example, age range, gender, medical condition). Include any local site restrictions, for example, “Enrollment at Partners will be limited to adults although the sponsor’s protocol is open to both children and adults.”

The study population will be screened from all patients diagnosed with PNES in Brigham and Women’s Hospital by capture of a definitive event on video EEG without EEG correlate. Patients with a mixed diagnosis of both PNES and epileptic seizures will be included. Pediatric patients (under age 18) are not typically evaluated by EEG in our hospital and will therefore be excluded. Patients with estimated IQ<70, inability to speak fluently in English or Spanish, active substance use disorder, pregnancy, or active medical issues which would preclude participation in weekly psychotherapy will be excluded. Patients meeting inclusion criteria will be considered eligible and will be approached for this study whether or not they are also enrolled in PHRC IRB protocol 2013P000133 (we anticipate that most eligible patients will be enrolled in both protocols).

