Our goal will be to enroll 60 patients diagnosed with PNES, with 30 randomized to the treatment arm (motivational interview) and 30 randomized to the control arm (informational interview).

Potential subjects will be asked if they are willing to meet with study staff by a member of the clinical team during their inpatient admission. If the patient is willing, they will be approached during their admission by a member of the study staff. The recruiter will not be a member of the treatment team, and in all cases the recruiter will clearly specify that the patient will receive the same standard-of-care treatment for PNES (initial clinical follow-up with neuropsychiatrist and epileptologist and psychotherapy from a licensed therapist) whether or not they participate in the study.

The purpose and structure of the study will be described, and if the individual is interested than the full informed consent process will completed, including detailed review of all potential risks and benefits- Because the informed consent process will be completed during an inpatient admission, time constraints will be minimized and the patient will have ample time to consider his or her consent. If informed consent is obtained, then study procedures will begin.

Baseline demographic data, psychiatric comorbidities, quality of life, and healthcare resource utilization will be recorded in the EMU and the patient will be randomized to treatment (standard treatment + motivational interviewing) vs. control (standard treatment only). The patient will be scheduled for an initial appointment in the “long-term monitoring clinic” with an epileptologist and a neuropsychiatrist (part of standard care for PNES at BWH). At the end of this clinic appointment the patient will have either a motivational interview (treatment) or informational interview (control) depending on their randomization. They will then be referred for weekly psychotherapy either at BWH or with a local provider (again, part of standard care for PNES at BWH). After 4 months they will be called and have a phone interview regarding their adherence to treatment, their reasons for adherence or non-adherence, seizure frequency, quality of life, and healthcare resource utilization over the prior 3 months.

Briefly describe study procedures. Include any local site restrictions, for example, “Subjects enrolled at Partners will not participate in the pharmacokinetic portion of the study.” Describe study endpoints.

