Baseline demographic data, psychiatric comorbidities, seizure frequency, quality of life, and healthcare resource utilization will be recorded following enrollment during the inpatient stay as part of PHRC IRB protocol 2013P000133. If the patient is not enrolled in protocol 2013P000133, baseline demographic data, seizure data, psychiatric comorbidities, qualities of life and healthcare resource utilization will be collected during the admission at which the patient is diagnosed, as detailed in appendix 1. All enrolled subjects will be scheduled for an initial appointment in the joint psychiatry-neurology clinic with a board certified neuropsychiatrist and board certified neurologists, which is standard of care for newly diagnosed PNES patients at Brigham and Women’s Hospital.

All subjects will attend the initial clinic visit with the neuropsychiatrist and epileptologist. At the end of this visit, those subjects randomized to motivational interviewing will be questioned using standardized motivational interviewing techniques by the study author who is a board certified neurologist and who will have formal training and certification in motivational interviewing. Motivational interviews will include the classical 4 steps of MI: 1) engagement (in which the patient’s goals and interests are elicited and the therapeutic alliance is established); 2) focusing (in which the specific subjects of discussion and intervention are negotiated); 3) strengthening motivation (in which the patients’ reasons for healthcare intervention are made explicit, discussed, and reinforced); and 4) planning (in which actions for healthcare intervention are planned out based on the patients’ own goals and interests).

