All subjects will be contacted by phone at 4 month follow-up. If necessary they will be called 5 times at various times during the day and early evening. If they are not reached, they will receive a letter requesting them to contact the study staff to complete the study. Subjects will be questioned about their adherence to treatment. The primary outcome will be the number of psychotherapy sessions for the treatment of PNES in which they have participated over the past three months. They will also be assessed for secondary outcomes including dichotomous adherence (either seizure freedom or active participation in psychotherapy for the treatment of PNES, with more than 5 sessions over the past 3 months), seizure frequency over the past month, number of hospitalizations and emergency department visits over the past 3 months, and quality of life as measured by the brief QOLIE-10 instrument. For those patients who give permission, their psychotherapists will be contacted by study staff to confirm the exact number of psychotherapy sessions over the past 3 months. A standard Partners clinical records release form with the patient’s signature will be sent to the therapist’s office.

Biostatistical Analysis:

A) Motivational Interviewing Treatment Integrity

Fidelity to motivational interviewing techniques during motivational interviewing sessions (intervention arm) will be assessed by blinded reviewers using the Motivational Interviewing Treatment Integrity code (MITI) 4.0. Relational scores and technical scores of ≥ 4 will be taken as indicating adherence to motivational interviewing techniques. Conversely abstinence from motivational interviewing techniques during informational interviews (control arm) will also be assessed by blinded reviewers using the MITI 4.0. Relational scores and technical scores of ≤ 2 will be taken as indicating abstinence from motivational interviewing techniques.

B) Outcome data

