Outcome data collected during study, collected at 4 month follow-up, includes seizure frequency over the past 3 months, number of emergency department visits over the past 3 months, QOLIE-10 score (see attached instrument), and participation in psychotherapy for the treatment of PNES (and number of sessions over the past 3 months). The primary outcome will be adherence, defined as attending 8 or more psychotherapy sessions over the past 3 months. Secondary outcomes will include decrease in PNES frequency, seizure freedom, change in QOLIE-10 score, and change in monthly ED visits.

Intergroup comparisons will be made between the treatment arm (motivational interviewing) and control arm (informational interviewing) using the t-test or Wilcoxon rank-sum test depending on normality of distributions.

C) Power analysis:

Sample size of 30-per-arm was calculated to detect a difference in adherence of 25% vs. 60% with power of 0.80 and alpha of 0.05.

For studies involving treatment or diagnosis, provide information about standard of care at Partners (e.g., BWH, MGH) and indicate how the study procedures differ from standard care. Provide information on available alternative treatments, procedures, or methods of diagnosis.

All patients enrolled in study will still receive standard of care for patients diagnosed with PNES at Brigham and Women's Hospital: initial clinical follow-up with neuropsychiatrist and epileptologist and psychotherapy from a licensed therapist. Study patients will additionally receive either an informational interview (control arm) or a motivational interview (treatment arm) following their initial clinic follow-up.

Describe how risks to subjects are minimized, for example, by using procedures which are consistent with sound research design and which do not unnecessarily expose subjects to risk or by using procedures already being performed on the subject for diagnostic or treatment purposes.

Research procedures (motivational interviewing vs. informational interview) are consistent with sound research design. Motivational interviewing has been studied and used for years in promoting abstinence from substance abuse and adherence with treatment in other disorders (HIV, schizophrenia, etc.), and is thought to be associated with minimal risk.

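### Psychotherapy attendance that predates the interview can count as adherence in both arms, and the plan neither names it at baseline nor adjusts for it

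*Combined protocol and SAP*

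**What the plan says.** On entry by video-EEG diagnosis, the eligibility paragraph of Research Design and Methods states: "The study population will be screened from all patients diagnosed with PNES in Brigham and Women’s Hospital by capture of a definitive event on video". The exclusions cover IQ, language and the following: "active substance use disorder, pregnancy, or active medical issues which would preclude participation in weekly psychotherapy will be excluded". None refers to psychotherapy already under way.

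Baseline data are described twice in the same section. The design summary says: "Baseline demographic data, psychiatric comorbidities, quality of life, and healthcare resource utilization will be recorded in the EMU". The study procedures say: "Baseline demographic data, psychiatric comorbidities, seizure frequency, quality of life, and healthcare resource utilization will be recorded following enrollment during the inpatient stay", under the companion protocol. For patients outside that protocol the same domains "will be collected during the admission at which the patient is diagnosed, as detailed in appendix 1". Neither list names psychotherapy.

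The primary outcome also appears twice. The study procedures give a count: "The primary outcome will be the number of psychotherapy sessions for the treatment of PNES in which they have participated over the past three months". Part B (Outcome data) of the Biostatistical Analysis gives a binary outcome: "The primary outcome will be adherence, defined as attending 8 or more psychotherapy sessions over the past 3 months". The binary sentence has no limit to PNES-directed sessions, although the opening sentence of that paragraph describes the item collected as psychotherapy for PNES. Part B then plans a t-test or Wilcoxon rank-sum comparison of the arms, with no covariate or stratification. Part C (Power analysis) gives 30 per arm for 25% vs 60%, power 0.80, alpha 0.05.

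**The concern.** The design summary refers patients to weekly psychotherapy after the interview, so the effect sought is on attendance after that point. Attendance in the months before enrolment is the baseline value of the primary outcome and probably its strongest predictor. A patient who enters with an established therapist, most plausibly for a psychiatric comorbidity, may go on to 8 or more sessions in 3 months without any change due to the interview.

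Such patients raise the adherence rate in both arms and carry little information about the interview. They shrink the expected difference and, in arms of 30, can fall unevenly by chance. A design set at exactly 0.80 power has no margin for this, and the stated analysis would not separate the effect of the interview from the mix of patients.

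**Working it through.** **Inputs.** From Part C: 25% vs 60%, power 0.80, alpha 0.05 (taken as two-sided, since the plan does not say), 30 per arm. The share f of patients already attending psychotherapy is not in the documents. I assume 5% to 30%.

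**The plan's own figure.** With pooled variance and no continuity correction:

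n = [1.960·√(2·0.425·0.575) + 0.842·√(0.25·0.75 + 0.60·0.40)]² / 0.35² = (1.3702 + 0.5503)² / 0.1225 = 30.1, so 31 per arm.

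The arcsine formula gives 29.9, so 30. Power at 30 per arm is Φ[(0.35·√30 − 1.3702)/0.6538] = Φ(0.836) = 0.80. The stated sample size reproduces.

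**Reading A: 25% and 60% describe patients not yet in therapy, and every prior attender reaches 8 sessions in both arms.** Each arm's rate becomes f + (1 − f)·p. For f = 10%: 0.10 + 0.90·0.25 = 32.5% and 0.10 + 0.90·0.60 = 64.0%. Power is Φ[(0.315·√30 − 1.960·0.7067)/0.6707] = Φ(0.507) = 0.69. The same steps give:

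| Share f (assumed) | Control | Motivational interview | Difference (points) | Power, 30 per arm | n per arm for 0.80 |
|---|---|---|---|---|---|
| 0% | 25.0% | 60.0% | 35.0 | 0.80 | 31 |
| 5% | 28.75% | 62.0% | 33.25 | 0.75 | 34 |
| 10% | 32.5% | 64.0% | 31.5 | 0.69 | 39 |
| 20% | 40.0% | 68.0% | 28.0 | 0.59 | 49 |
| 30% | 47.5% | 72.0% | 24.5 | 0.49 | 62 |

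If only 80% of prior attenders reach 8 sessions in each arm, the rates are 0.8f + (1 − f)·p, and power is 0.70, 0.59 and 0.48 at 10%, 20% and 30%. The loss arises because the interview does not change their outcome. It does not require that all of them succeed.

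**Reading B: 25% and 60% are whole-population rates that already include prior attenders.** Power stays at 0.80. If prior attenders always succeed, the rates needed in the others are (0.25 − f)/(1 − f) and (0.60 − f)/(1 − f). At f = 10% this is 0.15/0.90 = 16.7% rising to 0.50/0.90 = 55.6%. At f = 20% it is 0.05/0.80 = 6.25% rising to 0.40/0.80 = 50%. Under this reading f cannot exceed 25%.

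**Chance imbalance.** With two independent binomial counts (30, f), the arms differ by 4 or more prior attenders with probability 0.13 at f = 10% and 0.26 at f = 20%. Four patients are 4/30 = 13 points of an arm.

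**What adjustment recovers under Reading A.** When prior attenders all succeed, their stratum carries no information and the comparison rests on 30·(1 − f) per arm. That is 27 per arm and power 0.75 at f = 10%, and 24 per arm and power 0.70 at f = 20%, against 0.69 and 0.59 unadjusted. A simulation of the same model agrees to within about 0.02. The recovery is partial and would be smaller if prior attenders do not all succeed.

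**The case against.** Several stronger conclusions are tempting, and the documents do not support them.

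- **Any psychotherapy counts.** A reader could infer this from the binary definition alone. The opening sentence of the same paragraph and the study procedures both limit the item to PNES treatment. The fault is a missing qualifier in the one sentence a scorer would apply, not a stated all-inclusive rule. Even with the qualifier, no rule says how to classify sessions with an existing therapist.
- **Prior attendance is recorded nowhere.** This cannot be established. Healthcare resource utilization is a listed domain, and the detail sits in appendix 1 and the companion protocol, neither of which is available here. The companion protocol holds Aim 1, on baseline correlates of non-adherence, and most patients are expected to be in both studies. What stands is that no listed domain names attendance, and the analysis would not use it if it were recorded.
- **The trial is biased towards one arm.** Randomisation balances prior attenders on average.
- **Such patients should be excluded.** Aim 3 concerns adherence to treatment, which includes staying in therapy as well as starting it, so broad entry is a defensible choice. Excluding 10% to 30% of candidates at one site seeking 60 would not be a small loss. A limit to patients diagnosed at the index admission would add little. Consent follows the diagnosis during the admission (Recruitment Procedures), and the clinic visit is described as one "which is standard of care for newly diagnosed PNES patients at Brigham and Women’s Hospital".

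That last point also bears on size. Therapy aimed at PNES before entry should be uncommon, so f may be small. Long duration since onset appears in Hypothesis 1, which belongs to the companion protocol, and onset is not diagnosis.

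**Conclusion.** The point holds as a gap in design and analysis. Nothing in eligibility, the named baseline domains or the planned comparison deals with psychotherapy that predates the interview, and the binary primary definition is looser than the text around it. The consequence is a diluted difference and unadjusted chance imbalance. Its size is hypothetical because the share is undocumented. Power is about 0.75 to 0.49 for shares of 5% to 30% if the planning rates describe patients not yet in therapy, and unchanged at 0.80 if they describe everyone. Part C does not say which. The case for acting rests on the low cost of the remedy and on the value of having the baseline of the primary outcome, not on any one of these figures.

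**What to change.** 1. Before randomisation, record the number of psychotherapy sessions in the 3 months before admission and the indication for each course of therapy. If appendix 1 and the companion protocol already do this, say so in the protocol. Asking at the 4-month call instead would rely on recall after the intervention.
2. Adjust the primary comparison for prior attendance. For the binary outcome, a Cochran-Mantel-Haenszel test stratified by attendance at entry (yes/no) is suitable. Ordinary logistic regression may fail if every prior attender is adherent. If the count is kept as primary, use the prior count as a covariate.
3. In Part B, limit the sessions that count towards the threshold of 8 to those for the treatment of PNES, as in the study procedures, and state how sessions with a therapist seen before enrolment are classified.
4. In Part C, state whether 25% and 60% include patients already in therapy.

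No change to eligibility is needed. The cost is one baseline question, one covariate in a 60-patient analysis and a few words of definition.

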**PARTNERS HUMAN RESEARCH COMMITTEE
PROTOCOL SUMMARY**

Answer all questions accurately and completely in order to provide the PHRC with the relevant information to assess the risk-benefit ratio for the study. Do not leave sections blank.

PRINCIPAL/OVERALL INVESTIGATOR

[name]

PROTOCOL TITLE

Motivational interviewing to enhance adherence of patients with psychogenic non-epileptic seizures: a model of patient engagement in functional neurological symptom disorders

FUNDING

Practice Research Training Fellowship (American Academy of Neurology, American Brain Foundation)

VERSION DATE

July 8th, 2015

SPECIFIC AIMS

Concisely state the objectives of the study and the hypothesis being tested.

NB: Specific Aims 1 and 2 pertain to the first part of this project, detailed under BWH IRB protocol 2013P000133. Specific Aim 3 pertains to the second part of this project, detailed here.

Aim 1: To identify the baseline characteristics which correlate most closely with non-adherence to treatment in patients with PNES.

Hypothesis 1: Factors including low income, low educational achievement, unmarried status, lack of access to transportation, presence of psychiatric comorbidities, high seizure frequency, and long duration since onset of PNES will correlate with non-adherence in patients with PNES.

Aim 2: To identify the factors to which non-adherent patients with PNES attribute lack of adherence.

Hypothesis 2: Patients will most frequently attribute their lack of adherence to external factors including ineffective treatment, lack of empathy on the part of their physicians, and difficulty arranging transportation or time away from work/childcare. Patients will not attribute non-adherence to internal factors such as ambivalence about treatment, avoidance, help-rejection, or psychiatric comorbidities.

Aim 3: To determine whether motivational interviewing improves adherence to treatment (primary outcome), seizure frequency, healthcare usage, and quality of life (secondary outcomes).

Hypothesis 3: A brief in-person interview, using motivational interviewing techniques, will improve adherence, seizure frequency, healthcare usage, and quality of life at 4-month follow-up among patients with PNES when compared to a control group receiving only informational interviewing.

BACKGROUND AND SIGNIFICANCE

Provide a brief paragraph summarizing prior experience important for understanding the proposed study and procedures.

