The initial clinic visit and subsequent interview will be recorded with the patients’ consent, and blinded reviewers hired through the department of psychiatry, trained and certified in motivational interviewing, will score the audio recordings using the Motivational Interviewing Treatment Integrity code (MITI) 4.0 to assess fidelity to standardized motivational interviewing techniques. Recordings and blinded review of interviews are for the sole purpose of ensuring that the interviewer is in fact using proper interviewing techniques (ie motivational interviewing techniques for patients in the motivational interviewing arm and abstinence from motivational interviewing techniques in the control arm). Such recordings and review are recommended in motivational interviewing research.

Those subjects randomized to the control group will also undergo an initial clinic visit with a neuropsychiatrist and neurologists – again recorded with the subjects’ consent and scored using the MITI 4.0 to assess abstinence from motivational interviewing techniques. However they will not undergo any subsequent motivational interview. Following the initial clinic visit, all subjects with ongoing seizures will either be scheduled for ongoing psychotherapy for treatment of PNES at Brigham and Women’s Hospital or referred to a local psychotherapist according to their preference.

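### The plan names two different primary outcomes, a session count and attendance at 8 or more sessions, and no rule says which governs

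*Combined protocol and SAP*

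**What the plan says.** All the text is in the combined protocol and SAP, and all of it is current.

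- **Research Design and Methods, study procedures (4-month phone contact):** "The primary outcome will be the number of psychotherapy sessions for the treatment of PNES in which they have participated", counted over three months. The same paragraph lists a dichotomous adherence measure as secondary: "either seizure freedom or active participation in psychotherapy for the treatment of PNES, with more than 5 sessions over the past 3 months".
- **Biostatistical Analysis, B) Outcome data:** "The primary outcome will be adherence, defined as attending 8 or more psychotherapy sessions over the past 3 months". Here the number of sessions appears among the data collected but not among the outcomes to be analysed.
- **Same section, tests:** group comparisons will be made "using the t-test or Wilcoxon rank-sum test depending on normality of distributions". No test is named specifically for a yes/no outcome.
- **Part C of the same section, on power:** "Sample size of 30-per-arm was calculated to detect a difference in adherence of 25% vs. 60% with power of 0.80 and alpha of 0.05". The sentence does not say which definition of adherence the two rates describe.
- **Specific Aims, Aim 3:** "To determine whether motivational interviewing improves adherence to treatment (primary outcome"; it gives neither a scale nor a cut-off.

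The plan also describes referral in two ways. The design summary is unconditional: "They will then be referred for weekly psychotherapy either at BWH or with a local provider". The later procedures text is limited to patients still having seizures: "Following the initial clinic visit, all subjects with ongoing seizures will either be scheduled for ongoing psychotherapy for treatment of PNES".

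**The concern.** A count and a cut of that count are different endpoints, with different effect measures, different power and possibly different conclusions. The procedures text treats a binary adherence measure as secondary. The analysis text makes another binary measure primary. One statement therefore cannot be read as shorthand for the other.

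Both versions come from the same follow-up data, so the choice between them could be made after the results are seen. If either could be claimed at 0.05, the error rate would exceed 5%. The stated power of 0.80 also applies to proportions and does not carry over to the count.

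**Working it through.** **1. The definitions side by side**

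| Patient at 4 months | Count (primary, study procedures) | 8 or more sessions (primary, analysis section) | Seizure-free or more than 5 sessions (secondary) |
|---|---|---|---|
| 6 or 7 sessions, ongoing seizures | 6 or 7 | non-adherent | adherent |
| Seizure-free, fewer than 8 sessions | as counted | non-adherent | adherent |
| 8 or more sessions | as counted | adherent | adherent |

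Under the conditional referral text, a subject who is seizure-free at the clinic visit might not be referred. That subject would then count as non-adherent under the 8-session rule.

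**2. Reproducing the plan's sample size**

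Inputs from C) Power analysis: 25% vs. 60%, power 0.80, alpha 0.05. Sidedness is not stated; two-sided is assumed.

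Pooled two-proportion formula without continuity correction, with mean proportion (0.25 + 0.60)/2 = 0.425:

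n = [1.960 × √(2 × 0.425 × 0.575) + 0.842 × √(0.25 × 0.75 + 0.60 × 0.40)]² / 0.35²

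= [1.960 × 0.699 + 0.842 × 0.654]² / 0.1225 = 30.1 per arm

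This rounds up to 31, and the same formula gives power 0.799 at 30 per arm. The plan's figure therefore reproduces as a binary calculation. A one-sided formula with continuity correction also gives 30, so the match does not settle sidedness.

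Exact enumeration of all 2×2 tables at 30 per arm, two-sided 0.05:

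| Test on the yes/no outcome | Power, 25% vs. 60% | Null rejection, 25% vs. 25% |
|---|---|---|
| Uncorrected chi-square | 0.802 | 0.049 |
| t-test on 0/1 data | 0.802 | 0.049 |
| Wilcoxon on 0/1 data | 0.802 | 0.049 |
| Fisher's exact | 0.719 | 0.025 |

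Fisher's test reaches 0.797 at 36 per arm and 0.815 at 37. The absence of a named binary test is therefore a minor matter, unless Fisher's test is the one used.

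**3. Power if the count governs**

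The documents give no mean, SD or distribution of sessions, so no required size can be derived. Under a normal approximation, 30 per arm gives 80% power only for a standardized difference of (1.960 + 0.842) × √(2/30) = 0.72. Assumed differences show the range:

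| Standardized difference (assumed) | Power at 30 per arm | Needed per arm for 0.80 |
|---|---|---|
| 0.5 | 0.49 | 63 |
| 0.6 | 0.64 | 44 |
| 0.8 | 0.87 | 25 |

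A second check fixed the proportions with 8 or more sessions at 25% and 60% and simulated 12 assumed count shapes, 20,000 trials each. Power was 0.64 to 0.96 (Wilcoxon) and 0.60 to 0.97 (t-test). In a constructed extreme, where the intervention only moves patients from 5–7 to 8–9 sessions, Wilcoxon power was 0.21.

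**4. Error rate if both versions are tested and either may be claimed**

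Upper reference, if the two tests were independent: 1 − 0.95² = 0.0975. They are positively correlated, so the rate was simulated with no treatment effect, 30 per arm and 13 weekly slots. All distributions are assumed.

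- Some patients with zero sessions, the rest binomial(13) with a beta(2, 1.2) probability; 6,000 trials each. Wilcoxon or chi-square rejected in 7.5%, 7.5% and 7.4% of trials with 20%, 40% and 60% at zero.
- Nine other zero-inflated beta-binomial models with 12–25% attending 8 or more; 20,000 trials each. Wilcoxon or chi-square rejected in 7.8–9.3%, t-test or chi-square in 7.3–8.8%. Each test alone rejected in 4.7–5.7%. About 9–14% of patients had 6 or 7 sessions.
- Four further zero-inflated models gave 8.0–9.7%.

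**The case against.** The best defence is that the plan can be read as having one primary outcome. The section headed as the statistical analysis names attendance at 8 or more sessions, and the power statement in proportions follows directly. That is the natural reading, but it remains an inference. The power sentence names no cut-off, the only tests named suit a count at least as well, and the procedures text is equally explicit that the count is primary.

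Several narrower objections stand:

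- The error inflation is conditional. Nothing in the plan says both versions will be tested or that either may be claimed, and the percentages depend on assumed distributions.
- The range of count power is too wide to show that the count is weak; it can exceed 0.80. The supported statement is that its power is unspecified.
- A secondary outcome may use a different cut-off from the primary. The rule of more than 5 sessions or seizure freedom is not itself an error.
- The seizure-free case is uncertain. The standard-of-care text says all enrolled patients receive psychotherapy as part of usual care, and no figure says how many would be seizure-free at the clinic visit. This is a point to clarify, not the main ground.
- Preferring chi-square to the t-test on 0/1 data changes nothing in power.

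None of these removes the conflict between the two primary-outcome statements.

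**Conclusion.** The concern holds and must be fixed. Two current sections assign primary status to different endpoints, with no precedence, co-primary or multiplicity rule. This is a contradiction, not merely missing detail. The sample-size arithmetic is sound for a binary outcome if alpha is two-sided, and it gives no support for the count. The conclusion rests on the text itself; the 7% to 10% error rate and the count-power figures illustrate the stakes under assumed session distributions.

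**What to change.** 1. State one primary outcome in identical words in the study-procedures text and in B) Outcome data, and word Aim 3 to match.
2. Attending 8 or more sessions is the version consistent with the power statement. If it is kept, say that the 25% and 60% refer to it and that alpha is two-sided. Name the uncorrected Pearson chi-square test, and report the risk difference with a 95% confidence interval. Fisher's exact test should not be offered unless power is restated.
3. Make the session count a secondary outcome with a pre-set Wilcoxon test. Label the measure based on more than 5 sessions or seizure freedom clearly as secondary or as a sensitivity analysis.
4. Reconcile the two referral statements, and state how seizure-free subjects are classed in the primary outcome.
5. If the count is preferred as primary, restate the power with a justified mean difference and SD or an assumed distribution.

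**Cost:** with the 8-session version and the chi-square test, the change is wording only, with no new data and no change to 30 per arm. That size assumes complete follow-up: 0.802 leaves almost no margin, and the power analysis states no allowance for loss. The sponsor gives up the freedom to choose between versions. If seizure freedom is credited in the primary, the 25% and 60% must be justified again for that definition.
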